### **Replacement Policy**

Patients will not be replaced. Based on prior experience, we anticipate that we can comfortably accrue 36 patients per year and complete the study within 2 years.

#### **14.4 Evaluation of Safety**

In light of the well reported safety of escitalopram, there will be no statistical aspect to safety review. We will closely measure side effects as part of this clinical trial, but will not specifically have this as a secondary endpoint, since escitalopram has been studied extensively in patients, and even as a prophylactic antidepressant in the cancer population. Standard toxicity recording will be performed through phone interviews at monthly intervals at a minimum, using the CTCAE 5.0 grading system.

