## **Benefits**

Potential benefits of the study for the patient include prevention of depression, improved quality of life, and improved cancer survival. For the field, the study may demonstrate that prophylactic anti-depressant use is beneficial and provide a justification for a larger, phase III trial.

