## 8.2 Definitions

### 8.2.1 Adverse Event

An **adverse event** (AE) is any unfavorable or unintended event, physical or psychological, associated with a research study, which causes harm or injury to a research participant as a result of the participant's involvement in a research study. The event can include abnormal laboratory findings, symptoms, or disease associated with the research study. The event does not necessarily have to have a causal relationship with the research, any risk associated with the research, the research intervention, or the research assessments.

Adverse events may be the result of the interventions and interactions used in the research; the collection of identifiable private information in the research; an underlying disease, disorder, or condition of the subject; and/or other circumstances unrelated to the research or any underlying disease, disorder, or condition of the subject.

The measurement of side effects of escitalopram is not an endpoint of this study and escitalopram has been studied extensively in patients. This drug has also been studied as prophylactic antidepressant in the cancer populations. All patients enrolled to this study will be receiving chemotherapy at the time of treatment and will be under clinical care during this interval. Adverse events attributed to chemotherapy and/or underlying disease will not be recorded for this study.

Akathisia, or restlessness, is a serious but uncommon side effect, which patients will be alerted to report. Other common side effects typically go away on their own. Patients will be educated on possible symptoms, as is routinely done when patients are started on an anti-depressant off-of trial. They will contact the PI if the symptom becomes debilitating and referred to psychiatry for consideration of removal from the study.

Suicidal ideation will be queried every 2 weeks and prompt an immediate referral to psychiatry.

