### **8.2.3 Adverse Event Evaluation**

The investigator or designee is responsible for ensuring that all adverse events, (both serious and non-serious as defined in previous sections) observed by the study staff or reported by the subject that are determined to be related or possibly related to escitalopram/placebo which occur after the initiation of escitalopram/placebo are fully recorded in the subject's medical record and reported according to AE reporting policies of the IRB of record. Adverse events attributed to chemotherapy and/or underlying disease will not be recorded for this study. Source documentation must be available to support all adverse events.

The investigator or sub-investigator (treating physician if applicable) will provide the following for all adverse events (both serious and non-serious):

- Event term (as per CTCAE)
- Description of the event
- Date of onset and resolution
- **Expectedness of the toxicity**
- **Grade of toxicity**
- **Attribution of relatedness to the investigational agent- (this must be assigned by an investigator, sub-investigator, or treating physician)**
- Action taken as a result of the event, including but not limited to; no changes, dose interrupted, reduced, discontinued, etc. or action taken with regard to the event, i.e. no action, received conmed or other intervention, etc.
- Outcome of event

Descriptions and **grading scales** found in the NCI Common Terminology Criteria for Adverse Events (CTCAE) version **5.0** will be utilized for AE reporting.

**An expected adverse event** is an event previously known or anticipated to result from participation in the research study or any underlying disease, disorder, or condition of the subject. The event is usually listed in the Investigator Brochure, consent form or research protocol.

**An unexpected adverse event** is an adverse event not previously known or anticipated to result from the research study or any underlying disease, disorder, or condition of the subject.

**Attribution** is the relationship between an adverse event or serious adverse event and the study drug. Attribution will be assigned as follows:

- Definite – The AE is clearly related to the study drug.
- Probable – The AE is likely related to the study drug.
- Possible – The AE may be related to the study drug.

- Unlikely – The AE is doubtfully related to the study drug.
- Unrelated – The AE is clearly NOT related to the study drug.

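### Section 14.4 plans no by-arm summary of tolerability, although the trial has a blinded placebo arm and already collects most of the data for one

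*Combined protocol and SAP*

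**What the plan says.** Section 14.4 says: "In light of the well reported safety of escitalopram, there will be no statistical aspect to safety review". It continues: "We will closely measure side effects as part of this clinical trial, but will not specifically have this as a secondary endpoint". Section 8.2.1 agrees: "The measurement of side effects of escitalopram is not an endpoint of this study".

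The analyses by randomized arm in Section 14.2 cover QIDS-SR, PHQ-9, FACT-Hep and overall survival. The outcome lists in Section 2.4 include no tolerability measure.

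The protocol nevertheless collects such data. The study calendar schedules FIBSER on Days 1, 8, 22, 36, 50, 64, 78 and 85 and at Week 25. Each pill diary in Appendix II has a daily bleeding column. Adverse events are graded by CTCAE 5.0 (Section 8.2.3). Section 8.2.4 requires serious bleeding, mania and suicidal ideation to be recorded. Section 7.0 governs stopping the drug.

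On attribution, Section 8.2.1 notes that "All patients enrolled to this study will be receiving chemotherapy at the time of treatment". Section 8.2.3 says of relatedness that "this must be assigned by an investigator, sub-investigator, or treating physician", and adds: "Adverse events attributed to chemotherapy and/or underlying disease will not be recorded for this study". The FIBSER form in Appendix VI tells patients to leave out effects they put down to medicines for other conditions.

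**The concern.** The side effects listed in Section 8.1 include nausea, diarrhea, fatigue, insomnia and dry mouth. In patients on chemotherapy, a clinician looking at one case, or a patient filling in a form, often cannot say which treatment caused such a symptom. A blinded, randomized comparison can show an excess in one arm without anyone having to decide. The trial has that comparison available and plans to use it for benefit only.

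This matters because of the intended use. Section 1.4 hopes that "the study may demonstrate that prophylactic anti-depressant use is beneficial and provide a justification for a larger, phase III trial", and Section 3.1 admits patients who are not depressed. A case for prophylaxis in such patients has to weigh benefit against harm, and a planner of the next trial would want counts by arm from this one.

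Early stops are the most exposed. Section 14.3 treats patients who stop the drug for a serious adverse event in the first four weeks as non-evaluable. For early stops because of an adverse event, Section 7.0 says both that the patient is no longer followed and that everyone who discontinues keeps completing questionnaires. A table of all randomized patients by arm would keep these patients in view.

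**Working it through.** **1. Denominators.** The documents give no safety figure to reproduce, so I start from the sample size. Section 14.3 wants 46 patients at 12 weeks with up to 15% attrition: 46 / (1 − 0.15) = 54.1, rounded up to 55, as stated. With 1:1 allocation (Section 3.1) I assume arms of 27 and 28.

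**2. Collected against planned.**

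| Data | Where collected | Summary by arm planned | Attribution needed first |
|---|---|---|---|
| FIBSER, 3 items | Calendar, Appendix VI | None | Yes, by the patient |
| Diary bleeding | Appendix II | None | No |
| Drug discontinuations | Sections 6.2, 7.0 | None | No, for a plain count |
| Events of special interest | Section 8.2.4 | None | Section 8.2.4 sets no such condition |
| Other adverse events | Section 8.2.3 | None | Yes, by the clinician |
| FACT-Hep | Calendar, Appendix V | Yes, scores at 12 weeks | No, for single symptoms such as nausea |
| Deaths | Section 14.2 | Yes, overall survival | No |

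**3. FIBSER forms.** The calendar has 9 time points, so at most 9 × 55 = 495 forms. Day 1 is baseline. Week 25 follows unblinding, which Section 6.1 places at the Day 85 visit. That leaves 7 on-study forms, at most 7 × 55 = 385. Day 85 counts as blinded only if the form is completed before the code is broken, and the text does not give the order.

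**4. Would the tables contain anything?** The chance of at least one event among 27 patients is 1 − (1 − p)^27. It is 0.99 at p = 15% (the nausea rate in Section 8.1), 0.75 at an assumed 5% and 0.24 at an assumed 1%.

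**5. Zero events.** The one-sided 95% upper bound for 0 of 27 is 1 − 0.05^(1/27) = 10.5%.

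**6. Precision of a difference.** The 95% half-width is 1.96 × √[(p0(1 − p0) + p1(1 − p1)) / 27], with assumed rates:
- 5% and 10%: 1.96 × √(0.1375/27) = 14 points
- 15% and 30%: 1.96 × √(0.3375/27) = 22 points
- 30% and 45%: 1.96 × √(0.4575/27) = 26 points
- 50% and 65%: 1.96 × √(0.4775/27) = 26 points

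**7. Would tests help?** Power for a 15-point excess (two-sided 0.05, 27 per arm, pooled normal approximation) is Φ[(0.15 − 1.96 × √(2p̄(1 − p̄)/27)) / √((p0(1 − p0) + p1(1 − p1))/27)], where p̄ is the mean of the two rates. For 15% against 30% this is Φ[(0.15 − 0.223)/0.112] = 26%. For control rates of 5%, 30% and 50% it is 38%, 20% and 20%. Estimates with intervals are sensible; tests are not.

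**The case against.** The strongest reply is that this is a disclosed and reasoned choice. The trial seeks preliminary evidence of efficacy, the drug is well studied, and about 27 patients per arm will say little about rare harms whatever is tabulated. Nothing in the plan contradicts itself here. All of that stands, and it limits the point to a reporting weakness. It does not remove it. Section 14.4 relies on outside evidence, and judging by the titles in the reference list, three of its five citations concern depressed patients, one is a gene-expression study in an esophageal adenocarcinoma model, and only one is a cancer trial. Section 1.2 describes that cancer trial's adverse effects for both treatment groups, which is the kind of statement this plan does not provide for.

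A reader might go further than the documents allow in four ways.

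- **That the data are collected for nothing.** Section 7.0 uses questionnaires and diaries to assess toxicity every two weeks, Table 7.1 ties bleeding grades to stopping the drug, and Section 14.2 has scores and adverse events reviewed within 24 hours. What is missing is an analysis.
- **That the trial will give no controlled information on harm.** FACT-Hep contains items on nausea, diarrhea, fatigue, dry mouth and sleep, and its scores are compared by arm, as is survival. The information is indirect and merged into scores. Some listed effects, such as somnolence and dizziness, have no FACT-Hep item of their own.
- **That comparison is forbidden.** The sentence rules out a statistical aspect. It does not bar a descriptive count, though it plans none.
- **That tables alone would settle causation.** Events attributed to chemotherapy or disease are not recorded, so an adverse-event table inherits the judgement that the comparison is meant to avoid. FIBSER carries a similar filter through the patient.

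The cancer center's monitoring plan and the annual committee report (Sections 8.6 and 8.7) might contain counts by arm, but the protocol does not describe any.

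**Conclusion.** The point holds as a cheap improvement to the plan. As written, a blinded placebo-controlled trial in patients who all receive chemotherapy plans no direct randomized summary of tolerability, although the data for a useful one are being collected. The primary analysis, sample size and power are untouched.

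The gain is modest. The bound of 10.5% and the half-widths of roughly 14 to 26 points rest on arms of about 27, a near-equal split and assumed event rates; only the 15% nausea rate comes from the documents. Such tables could show a large excess of a common effect and could not exclude an uncommon serious one. Diary bleeding, discontinuations and events of special interest would be the most informative, since they depend least on attribution. Tables of other adverse events and of FIBSER need the caveat printed with them.

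**What to change.** Replace the sentence in Section 14.4 with text to this effect:

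> Tolerability will be summarized for all randomized patients by assigned arm, including patients who stop treatment or are classed as not evaluable in the first four weeks. Drug discontinuations, events of special interest, diary bleeding, recorded adverse events (worst grade) and each of the three FIBSER items by visit will be tabulated, with between-arm differences and confidence intervals. No hypothesis tests will be done. Week 25 will be shown separately because patients are unblinded at Day 85. The FACT-Hep symptom items will be summarized by arm in the same way. Adverse-event tables contain only events not attributed to chemotherapy or disease, and FIBSER reflects the patient's own attribution.

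The two statements in Section 7.0 about follow-up after an early stop should be reconciled, so that the denominators by visit are known.

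The cost is a few tables from data already collected, with wide intervals that readers must be warned not to read as evidence of safety. Recording adverse events regardless of attribution would make the comparison stronger, but that is a separate decision. It changes Section 8 and data collection, so it is more than a change of wording in the analysis plan.

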**APPENDIX I**  
**PERFORMANCE STATUS CRITERIA**

ECOG Performance Status Scale		Karnofsky Performance Scale	
Grade	Description	Percent	Description
0	Normal activity. Full active, able to carry on all pre-disease performance without restriction.	100	Normal, no complaints, no evidence of disease.
		90	Able to carry on normal activity; minor signs or symptoms of disease.
1	Symptoms, but ambulatory. Restricted in physically strenuous activity, but ambulatory and able to carry out work of a light or sedentary nature (e.g., light housework, office work).	80	Normal activity with effort; some signs or symptoms of disease.
		70	Cares for self, unable to carry on normal activity or to do active work.
2	In bed < 50% of the time. Ambulatory and capable of all self-care, but unable to carry out any work activities. Up and about more than 50% of waking hours.	60	Requires occasional assistance, but is able to care for most of his/her needs.
		50	Requires considerable assistance and frequent medical care.
3	In bed > 50% of the time. Capable of only limited self-care, confined to bed or chair more than 50% of waking hours.	40	Disabled, requires special care and assistance.
		30	Severely disabled, hospitalization indicated. Death not imminent.
4	100% bedridden. Completely disabled. Cannot carry on any self-care. Totally confined to bed or chair.	20	Very sick, hospitalization indicated. Death not imminent.
		10	Moribund, fatal processes progressing rapidly.
5	Dead.	0	Dead

## **APPENDIX II**

### **SUBJECT PILL DIARY**

**Subject Name** \_\_\_\_\_ **Protocol #** CASE6220 **Subject Study ID** \_\_\_\_\_

**Weeks #: 1 and 2 (Days 1-14)**

#### **INSTRUCTIONS FOR THE SUBJECT:**

1. You will take one 10mg capsule of escitalopram/placebo each day. You should take your pill in the morning or evening. You may take the pill with or without food, as you wish.
2. Record the date, the number of tablets you took, and what time you took them.
3. If you have any comments or side effects please record them in the “Comments” column below.
4. If you have bleeding, please record in the “Bleeding” column below.
5. Please bring your pill bottle and this form to your physician when you come for your next appointment.
6. Please sign your name at the bottom of the diary.

Date	Day	# of 10mg pills and time taken	Comments	Bleeding
				Type of bleeding: nose bleed, cut that won't stop bleeding, bruising, blood in urine, red or black stool, Other (please describe) State if: Mild, Moderate, Severe
	(Wk 1) 1			
	2			
	3			
	4			
	5			
	6			
	7			
	(Wk 2) 8			
	9			
	10			
	11			
	12			
	13			
	14			
Subject's Signature: _____		Date: _____		

## SUBJECT PILL DIARY

Subject Name \_\_\_\_\_ Protocol # CASE6220 Subject Study ID \_\_\_\_\_

### Weeks #: 3 through 10 (Days 15 through 70) Page 1

#### INSTRUCTIONS FOR THE SUBJECT:

1. You will take two 10mg capsules of escitalopram/placebo each day. You should take your pill in the morning or evening. You may take the pill with or without food, as you wish.
2. Record the date, the number of tablets you took, and what time you took them.
3. If you have any comments please record them in the "Comments" column below.
4. If you have bleeding, please record in the "Bleeding" column below.
5. Please bring your pill bottle and this form to your physician when you come for your next appointment.
6. Please sign your name at the bottom of the diary.

Date	Day	# of 10 mg pills and time taken	Comments	Bleeding Type of bleeding: nose bleed, cut that won't stop bleeding, bruising, blood in urine, red or black stool, Other (please describe) State if: Mild, Moderate, Severe
	(Wk 3) 15			
	16			
	17			
	18			
	19			
	20			
	21			
	(Wk 4) 22			
	23			
	24			
	25			
	26			
	27			
	28			
	(Wk 5) 29			
	30			
	31			
	32			
	33			
	34			
	35			
	(Wk 6) 36			
	37			
	38			
	39			
	40			
	41			
	42			

Subject's Signature: \_\_\_\_\_ Date: \_\_\_\_\_

## SUBJECT PILL DIARY

Subject Name \_\_\_\_\_ Protocol # CASE6220 Subject Study ID \_\_\_\_\_

Weeks #: 3 through 10 (Days 15 through 70) Page 2

### INSTRUCTIONS FOR THE SUBJECT:

1. You will take two 10mg capsules of escitalopram/placebo each day. You should take your pill in the morning or evening. You may take the pill with or without food, as you wish.
2. Record the date, the number of tablets you took, and what time you took them.
3. If you have any comments please record them in the "Comments" column below.
4. If you have bleeding, please record in the "Bleeding" column below.
5. Please bring your pill bottle and this form to your physician when you come for your next appointment.
6. Please sign your name at the bottom of the diary.

Date	Day	# of 10 mg pills and time taken	Comments	Bleeding Type of bleeding: nose bleed, cut that won't stop bleeding, bruising, blood in urine, red or black stool, Other (please describe) State if: Mild, Moderate, Severe
	(Wk 7) 43			
	44			
	45			
	46			
	47			
	48			
	49			
	(Wk 8) 50			
	51			
	52			
	53			
	54			
	55			
	56			
	(Wk 9) 57			
	58			
	59			
	60			
	61			
	62			
	63			
	(Wk 10) 64			
	65			
	66			
	67			
	68			
	69			
	70			

Subject's Signature: \_\_\_\_\_ Date: \_\_\_\_\_

## SUBJECT PILL DIARY

Subject Name \_\_\_\_\_ Protocol # CASE6220 Subject Study ID \_\_\_\_\_

**Weeks #: 11 and 12 (Days 71-84)**

### INSTRUCTIONS FOR THE SUBJECT:

1. You will take one 10mg capsule of escitalopram/placebo each day. You should take your pill in the morning or evening. You may take the pill with or without food, as you wish.
2. Record the date, the number of tablets you took, and what time you took them.
3. If you have any comments or side effects please record them in the "Comments" column below.
4. If you have bleeding, please record in the "Bleeding" column below.
5. Please bring your pill bottle and this form to your physician when you come for your next appointment.
6. Please sign your name at the bottom of the diary.

Date	Day	# of 10mg pills and time taken	Comments	Bleeding
	(Wk 11) 71			Type of bleeding: nose bleed, cut that won't stop bleeding, bruising, blood in urine, red or black stool, Other (please describe) State if: Mild, Moderate, Severe
	72			
	73			
	74			
	75			
	76			
	77			
	(Wk 12) 78			
	79			
	80			
	81			
	82			
	83			
	84			

Subject's Signature: \_\_\_\_\_ Date: \_\_\_\_\_

## **APPENDIX III**

### **Clinical Medication Compliance Form for Investigational Studies**

**UH Seidman Cancer Center  
Clinical Trials Unit  
IDS Provided Agent Compliance form**

Pt Name: \_\_\_\_\_  
Pt MRN: \_\_\_\_\_  
(or place patient label here)

\* Calculate by: (Actual taken / # prescribed to take) X 100 = Comp.

Note: If need to document any discrepancies or issues with dosing, etc. use NTE or other clinical source documents.

### Varför inte?

## APPENDIX IV

### QIDS-SR16

#### The Quick Inventory of Depressive Symptomatology (16-Item) (Self-Report) (QIDS-SR16)

Name or ID: \_\_\_\_\_ Date: \_\_\_\_\_

#### CHECK THE ONE RESPONSE TO EACH ITEM THAT BEST DESCRIBES YOU FOR THE PAST SEVEN DAYS.

##### During the past seven days...

###### 1. Falling Asleep:

- 0 I never take longer than 30 minutes to fall asleep.
- 1 I take at least 30 minutes to fall asleep, less than half the time.
- 2 I take at least 30 minutes to fall asleep, more than half the time.
- 3 I take more than 60 minutes to fall asleep, more than half the time.

###### 2. Sleep During the Night:

- 0 I do not wake up at night.
- 1 I have a restless, light sleep with a few brief awakenings each night.
- 2 I wake up at least once a night, but I go back to sleep easily.
- 3 I awaken more than once a night and stay awake for 20 minutes or more, more than half the time.

###### 3. Waking Up Too Early:

- 0 Most of the time, I awaken no more than 30 minutes before I need to get up.
- 1 More than half the time, I awaken more than 30 minutes before I need to get up.
- 2 I almost always awaken at least one hour or so before I need to, but I go back to sleep eventually.
- 3 I awaken at least one hour before I need to, and can't go back to sleep.

###### 4. Sleeping Too Much:

- 0 I sleep no longer than 7-8 hours/night, without napping during the day.
- 1 I sleep no longer than 10 hours in a 24-hour period including naps.
- 2 I sleep no longer than 12 hours in a 24-hour period including naps.
- 3 I sleep longer than 12 hours in a 24-hour period including naps.

##### During the past seven days...

###### 5. Feeling Sad:

- 0 I do not feel sad.
- 1 I feel sad less than half the time.
- 2 I feel sad more than half the time.
- 3 I feel sad nearly all of the time.

#### Please complete either 6 or 7 (not both)

###### 6. Decreased Appetite:

- 0 There is no change in my usual appetite.
- 1 I eat somewhat less often or lesser amounts of food than usual.
- 2 I eat much less than usual and only with personal effort.
- 3 I rarely eat within a 24-hour period, and only with extreme personal effort or when others persuade me to eat.

- OR -

